2. Patient given QQs (FTND, QSU, HHWS, TAA, Treatment Satisfaction Survey) and QQ on smoking behavior/medication use. -can be done via text/e-mail if unable to come to clinic. Done after patient has seen providers.
3. Give patient \$40 and schedule next study visit.

6 Month Post-Treatment Follow-up:

1. If visit is in person, conduct CO test and document results in tracking log.
2. Patient given QQs (FTND, QSU, HHWS, TAA) and QQ on smoking behavior/medication use. -can be done via text/e-mail if unable to come to clinic. Done after patient has seen providers.
3. Give patient \$50.

Retention Procedures

Continue to attempt to reach the participant up to six months after the final follow-up visit. After the 6-month mark, the participant can be marked lost to follow-up.

Summary of Compensation

Timepoint	Compensation
Baseline	\$20
12 Week End of Treatment	\$40
1 mo Post-Treatment	\$40
3 mo Post-Treatment	\$40
6 mo Post-Treatment	\$50

Data Collection and Management

All study documentation will be kept in locked file cabinets in study personnel's offices at UAB, UW, and Fenway. The CNICS database can only be accessed by CNICS personnel using UAB, UW, and Fenway computers or encrypted laptops.

Data Analysis

Using Pearson's chi-square test for 2 independent proportions, we will analyze the difference in the proportion of participants with 7-day point-prevalence cessation at 6 months between the treatment arms. Participants for whom we do not have 6-month follow-up data will be assumed to be smoking. We do not anticipate any difference in baseline variables between arms, but if differences do exist, we will utilize a multivariate logistic regression model with cessation as the outcome, treatment group as the primary independent variable, and imbalanced variables which are known to be correlated with cessation as additional independent variables. The same approach will be taken for 24-hour quit attempt – dichotomized yes/no – at 6 months. For cigarette reduction, we will look at the change in number of cigarettes smoked per day at baseline and 6-month follow-up. Either a 2 independent sample *t*-test or the non-parametric Wilcoxon Rank-sum test as appropriate will be used to test for a difference in the change in cigarettes per day between the 2 groups. If necessary, an ordinary least squares regression model with change in cigarettes per day as the outcome adjusting for baseline

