In addition to these primary analyses, we will examine outcomes by sex and racial groups to determine moderator effects. For sensitivity analyses, we will exclude participants without 6-month follow-up data. We will also 1) consider count regressions models that can account for time from enrollment until 6 month visit (such as Poisson regression) if actual timing of planned 6-month follow-up visits differs enough between participants; 2) repeat all analyses using end of treatment and 6-month follow-up outcomes; 3) consider employing models that treat site as a clustering variable (such as Cochran-Mantel-Haenszel [41] and Generalized Estimating Equation); and 4) fit longitudinal models with data from all timepoints. These longitudinal models will examine the interaction between treatment group and time. Exploratory analyses will be conducted stratified by site, cigarettes per day at enrollment, and quit goal.

Protection of Human Subjects

Our team has devised a comprehensive plan for ensuring protection of human subjects throughout the course of the proposed study. We will utilize an English-language consent form with common phrasing that describes that no special privileges or considerations will be conferred because of study participation, and that access to medical care will not be affected by the potential participant's decision to enroll in the study. The procedures listed in the following sections detail procedures that have been approved and utilized during recent years of clinical and behavioral trials at each site for collaborative research that utilizes sensitive information from

participants. Our team will make every effort to protect all participants' confidential and private information in order to minimize possible study-associated risks.

All findings related to this research will be available and provided to study participants in accordance with standard practices. Clinical and measurement data used for research studies will be released only in de-identified fashion.

In addition, all study personnel are required to renew Human Subjects trainings annually, or in accordance with their site regulatory mandates.

Study Algorithm

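### No missing-data rule is given for change in cigarettes per day, so the stated test defaults to followed-up patients and its planned sensitivity analysis would repeat it

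*Combined protocol and SAP*

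**What the plan says.** Everything here is in the Combined protocol and SAP.

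- **Abstinence** (Data Analysis) is tested first: "Using Pearson's chi-square test for 2 independent proportions, we will analyze the difference in the proportion of participants with 7-day point-prevalence cessation at 6 months", followed by the rule "Participants for whom we do not have 6-month follow-up data will be assumed to be smoking".
- **Quit attempts** (Data Analysis): "The same approach will be taken for 24-hour quit attempt", so the rule carries over to this yes/no outcome.
- **Cigarette reduction** (Data Analysis): "For cigarette reduction, we will look at the change in number of cigarettes smoked per day at baseline and 6-month follow-up". A two-sample t-test or Wilcoxon rank-sum test "will be used to test for a difference in the change in cigarettes per day between the 2 groups". A regression is allowed if needed: "an ordinary least squares regression model with change in cigarettes per day as the outcome adjusting for baseline". That sentence breaks off in the text available to us. No value, imputation method or analysis set for missing patients appears before the break.
- **Sensitivity analyses** (end of Data Analysis): "For sensitivity analyses, we will exclude participants without 6-month follow-up data". Among further analyses, the plan will "fit longitudinal models with data from all timepoints" and examine the interaction of treatment with time.

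Aim 1 names cigarette reduction as one of three hypotheses at 6 months. The closing part of Data Analysis groups its test with the primary analyses, although Aim 1 attaches the label of primary outcome to confirmed abstinence.

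**The concern.** A patient lost before 6 months has a defined abstinence result but no defined change in cigarettes per day. Both stated tests need a number for each patient. With none assigned, the software drops the missing, and the same patient counts in one Aim 1 analysis and not in another. The exclusion analysis then has nothing to exclude for this outcome, so agreement between it and the main result would be automatic and would give no reassurance.

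The stake is a distorted arm difference if those who disappear differ in smoking from those who stay, and differ in a way that does not cancel between arms. That is plausible here. The arms are visibly different: only the intervention arm's providers receive a medication recommendation (Intervention Arm), and at UAB the study pays uncovered medication costs for intervention participants (Billing for Medication for Study).

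**Working it through.** **Inputs from the documents.** Target enrollment is 250 + 200 + 150 = 600; at 50/50 allocation that is 300 per arm. There is no figure for retention, SD of change, effect size, alpha or power, so there is no stated figure to reproduce. All other inputs below are assumptions, and tests are two-sided at 5%.

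**Step 1. Which patients each analysis uses.**

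- Abstinence and quit attempts: all randomized, missing scored by rule.
- Cigarette reduction: no rule, so by default those with a 6-month count.
- Cigarette reduction, exclusion sensitivity analysis: those with a 6-month count. This is the same set as the line above.

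**Step 2. When completers mislead.** Simulation of 4,000 trials with no true effect: mean change -5, SD 8 in both arms. Differences are AT minus eTAU, and negative favours AT.

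- Retention 85% vs 70%, dropout unrelated to change: bias 0.02, type I error 4.6%.
- Same retention, those who cut down less drop out more: bias +0.97, type I error 27.9%.
- 85% vs 75%, same mechanism: bias +0.65, type I error 15.3%.
- 80% in both arms, same mechanism in both: bias 0, type I error 5.0%.
- 80% in both arms, dropout related to change in AT only: bias -1.41, type I error 50.4%.

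The first and last lines show that unequal retention is neither sufficient nor necessary. What counts is how missingness relates to outcome in each arm.

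**Step 3. Size when dropout depends on the week-12 value.** Simulation of 4,000 trials, 300 per arm, no true effect, dropout logistic in week-12 change.

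- 30% (AT) vs 20% (eTAU) missing: completer bias -0.30, type I error 8.0%.
- 35% vs 20% missing: completer bias -0.43, type I error 11.4%.
- Imputing by arm from week-12 change: bias at most 0.01 in both, with the same SD of the estimate (0.55).

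A check by formula: rejection is about Φ(-1.96 + b/SE) + Φ(-1.96 - b/SE). With SE 0.55, b = 0.30 gives 8.5% and b = 0.43 gives 12.2%, close to the simulated values. Repeating the simulation with SD of change 6, correlation 0.6 between week-12 and 6-month change, and log-odds of dropout rising by 1 per SD gave -0.28 (7.9%) and -0.42 (11.1%). Other assumed inputs gave 0.34-0.51 with 8-12%. Hence a range of about 0.3-0.5 cigarettes/day.

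**Step 4. A harsher case.** Suppose every dropout is unchanged from baseline and the true all-randomized reduction is 0.80 × 4 = 3.2 in both arms, with 30% missing in AT and 20% in eTAU.

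- Completer reduction in AT: 3.2/0.70 = 4.57; in eTAU: 3.2/0.80 = 4.00; difference 0.57.
- SE = SD × √(1/210 + 1/240) = 0.57, 0.66, 0.76 for SD 6, 7, 8.
- Type I error: 17.2%, 13.9%, 11.8%.

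This is missing not at random. A missing-at-random analysis would not fully remove it.

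**Step 5. Missing set to baseline (zero change).** In the Step 2 simulation this gave bias -0.23 and type I error 6.7% at 85% vs 70% with outcome-related dropout in both arms. With dropout unrelated to outcome at the same retention, it gave bias -0.73 and type I error 22.8%. It is useful as a stress test and unsafe as the only method.

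**The case against.** The strongest reply is that the plan does not prescribe a completer-only test. Making exclusion of the missing a sensitivity analysis, with no limit to abstinence, suggests that the main analyses keep these patients. Eligibility requires at least 5 cigarettes a day, so a baseline count should exist for everyone and zero change could be assigned. A reader might infer that the test can only be run on completers; the documents do not support that. What stands is that no rule is stated, and a test on change without one falls back on observed values.

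A reader might also see a contradiction with the abstinence analysis. The smoking rule is never applied to cigarette counts, so this is a gap and a difference in analysis sets. Nor does unequal retention by itself bias the result, as Step 2 shows.

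Three further replies carry some weight. The regression sentence is cut off, so a rule may have followed; the point is limited to the available text. Text or e-mail completion at 6 months (Follow-up Visits) and up to six further months of contact attempts (Retention Procedures) should reduce missing counts. The longitudinal models could yield a 6-month contrast. However, they are listed as additional analyses, name no outcome and target the interaction with time, so they do not define the main estimate.

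**Conclusion.** The point holds as a gap with a better method available. For cigarette reduction, the available text leaves the missing-data handling undefined, the stated tests default to followed-up patients, and the planned exclusion analysis would then check nothing.

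The working size is a bias of about 0.3-0.5 cigarettes/day and type I error of 8-12% instead of 5%. This rests on 300 per arm, 30-35% versus 20% missing, and dropout driven by week-12 change. The 12-17% of Step 4 should not be read as what the fix would recover, because it assumes data missing not at random. If dropout is unrelated to outcome, or acts alike in both arms with equal retention, there is no bias. Confirmed abstinence, the labelled primary outcome, is not affected. The change should be made, but the trial's main conclusion does not depend on it.

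**What to change.** Before outcomes are examined by arm, state the following for change in cigarettes per day:

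1. **Main analysis on all randomized patients:** a mixed model with the 6-month arm contrast as the estimate, or multiple imputation by arm. Use the smoking data from baseline, week 12 and the 1- and 3-month post-treatment visits. This assumes that the smoking-behavior questionnaire at those visits records cigarettes per day; its items are not shown. It also takes 6 months as the 6-month post-treatment visit. Aim 1 counts from randomization, in which case the 3-month post-treatment visit (12 weeks plus 3 months) falls at about the outcome time and is not an intermediate visit.
2. **Secondary:** the completer-only t-test or rank-sum test, labelled as such.
3. **Sensitivity to data missing not at random:** missing set to baseline cigarettes per day, and a delta-adjusted analysis. Note that missing set to baseline can itself be biased when dropout is unrelated to outcome.
4. **Report retention by arm** at each visit.

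The cost is a change of wording and some extra programming, with no new visits or data. The downside is that the main estimate relies on a missing-at-random assumption, which the analyses in item 3 are there to test.

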Effectiveness of a Smoking Cessation Algorithm Integrated into HIV Primary Care

Study Protocol

NCT Number: NCT03670316

Date: September 10, 2025

Purpose and Background

Aim 1: Compare the efficacy of Algorithm Treatment (AT) to Enhanced Treatment as Usual (eTAU) control group for smoking cessation among PLWH smokers engaged in HIV clinical care. We hypothesize that the AT group will have a significantly higher proportion of abstinence (biochemically confirmed primary outcome), 24-hour quit attempts, and greater reduction in mean number of cigarettes smoked per day at 6-months post randomization compared to those in the eTAU group.

Aim 2: Characterize provider-, staff-, patient-, and clinic-level facilitators and barriers to integration of AT treatment and examine intervention cost effectiveness in care. We hypothesize that, compared to the eTAU, written pharmacological prescriptions for smoking cessation and provider knowledge and confidence to treat nicotine dependence will be significantly greater in the AT group. We will also describe clinic characteristics such as size, staffing patterns (e.g., number and type of staff, providers, etc.), average number of annual visits by patients, amount of Ryan White funding, and average appointment time to help inform a future wide-scale implementation project across all CNICS sites.

Aim 3: Estimate the cost effectiveness of the intervention relative to the primary smoking outcomes. This will be done by examining the incremental cost per quit of AT vs. eTAU at 3- and 6-months post intervention.

Site and Staff

The University of Alabama at Birmingham (UAB)

[name], Psy.D., Principal Investigator

[name], Co-Investigator

[name], Program Director
[name], Study Coordinator

The University of Washington (UW)

[name] Co-Investigator
[name], Study Coordinator

The Fenway Institute

[name], Co-Investigator
[name], Project Manager
[name], Study Coordinator

Eligibility Criteria & Approach

Eligibility:

CNICS PRO platform will indicate if the patient is eligible or not for the Algorithm study based on smoking scores.

Inclusion criteria:

1. Age 18 or older
2. Receiving HIV care at UAB, UW or Fenway
3. Smoking 5 or more cigarettes per day for the past month. Black and Milds and other cigars don’t count.

Exclusion criteria:

1. Cognitive impairment such that unable to provide informed consent.
2. Non-English speaking

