Carbon Monoxide Test

RA conducts test with participant immediately following consent. If the provider is waiting to see the participant, the CO test can be done after the visit. RA will instruct participant on how to use CO monitor and will step outside of the room while the participant blows into the monitor. Document the results in the tracking log.

Randomization

Randomization will be programmed into the CNICS PRO platform and will occur after the patient consents to the study. The randomization scheme is a 50/50 ratio between the intervention and control arms. Intervention vs. control status will be tracked in the PRO platform.

Intervention Arm:

Provider Confirmation

1. If the patient is in the intervention arm then:
 - a. The patient’s provider will be sent a note in the EMR or give a hard copy note describing which medication the algorithm recommends he/she prescribe the patient.
 - b. RC will send the physician the pharmacotherapy medication sheet (see Appendix) in the EMR for him/her to review the medication option derived from the algorithm, give him/her a hard copy of the pharmacotherapy medication sheet.

Both Arms:

Questionnaire Completion

Give patient additional questionnaires to complete on tablet in separate research room either before or after the visit with provider, depending on the clinic flow that day. If the participant can’t stay to complete the additional questionnaires, you can schedule a time for him to return to complete them, so long as he picks up his prescription at the pharmacy if the provider decides to prescribe him medication. This must be done on the same day as the baseline visit.

Questionnaires:

1. Demographics
2. Smoking Behavior/History
3. Hughes/Hatsukami Withdrawal Scale (HHWS)
4. Fagerstrom Test for Nicotine Addiction (FTND)
5. Questionnaire of Smoking Urges (QSU)
6. Thoughts about Abstinence (TAA)

Texting

Participants will be sent a text-message based survey each week (11 total) between the Initial Visit and the End of Treatment Visit (12 weeks post-Initial Visit). Response options will be listed after every question and participants will respond to the question with the letter or number included in parentheses. The questions below will be administered every week unless otherwise specified.

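### Covariate adjustment of the cessation analysis depends on observed baseline imbalance, no result is named as primary, and site is outside the primary test

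*Combined protocol and SAP*

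**What the plan says.** All of the analysis text is in the Data Analysis section of the combined protocol and SAP.

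- **Primary test:** "Using Pearson's chi-square test for 2 independent proportions, we will analyze the difference in the proportion of participants with 7-day point-prevalence cessation at 6 months". Participants without 6-month data count as smokers, so everyone randomized is analysed.
- **Adjustment:** "We do not anticipate any difference in baseline variables between arms, but if differences do exist, we will utilize a multivariate logistic regression model", whose covariates are treatment group plus "imbalanced variables which are known to be correlated with cessation as additional independent variables". No test or threshold for imbalance is given, no candidate covariates are listed, and precedence between the two results is not stated.
- **Quit attempts:** "The same approach will be taken for 24-hour quit attempt".
- **Site:** not in the primary test. Among the sensitivity analyses the plan will "consider employing models that treat site as a clustering variable (such as Cochran-Mantel-Haenszel [41] and Generalized Estimating Equation". A later sentence adds: "Exploratory analyses will be conducted stratified by site, cigarettes per day at enrollment, and quit goal".

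Elsewhere, the eligibility criteria require "Receiving HIV care at UAB, UW or Fenway", and the Enrollment section sets targets of 250, 200 and 150. On allocation, the Randomization section says: "The randomization scheme is a 50/50 ratio between the intervention and control arms". Patients are randomized individually after consent, and stratification by site is not mentioned.

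**The concern.** In a randomized trial, baseline differences between arms arise by chance. A rule that adjusts only when they are seen lets chance choose the estimate. A chi-square analysis targets a difference in proportions. A logistic model gives an odds ratio conditional on whichever covariates entered, and its meaning changes with that list. With no threshold, list or precedence, two analysts could follow the text and report different main results. A strong predictor that happens to balance is left out, although including it would help precision.

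Site is a fixed stratum: three named clinics, individual randomization, both arms at each. It is not a randomized cluster. Cochran-Mantel-Haenszel (CMH) treats it correctly, but the plan lists CMH as a clustering method, optional, next to a GEE that would have only three clusters. Robust GEE standard errors rely on many clusters.

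At stake are a main result that is not fixed in advance, a little precision, and a possible sensitivity analysis that could lend support to a false positive.

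**Working it through.** **Inputs.** From the documents: 250 + 200 + 150 = 600 patients, 1:1, so about 300 per arm; three sites; missing counted as smoking. The documents give no alpha, power, effect size or quit rates, so 600 has no derivation to reproduce. Assumed below: two-sided 5%; 10% v 18% quitting as the reference effect, OR = (0.18/0.82)/(0.10/0.90) = 1.98; covariate strengths and site rates as shown.

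**1. How often an imbalance trigger would fire.** If K independent covariates are screened at an assumed 5%, the chance of at least one flag in a perfectly randomized trial is 1 − 0.95^K:

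- K = 3: 14%
- K = 5: 23%
- K = 10: 40%

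Only covariates known to relate to cessation may enter, so the smaller K are the more relevant.

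**2. What the trigger does to error and power.** Simulated trials with K prognostic covariates, each with the stated log-OR per SD (4,000 to 5,000 replicates):

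| K, log-OR | Null error: if imbalanced | Null error: better of two picked | Power: never adjust | Power: if imbalanced | Power: always adjust |
|---|---|---|---|---|---|
| 5, 0.2 | 4.9% | 5.1% | 80.6% | 80.9% | 81.3% |
| 5, 0.3 | 4.8% | 5.1% | 81.3% | 81.2% | 83.0% |
| 10, 0.2 | 4.9% | 5.3% | 81.2% | 81.0% | 82.6% |
| 3, 0.5 | 4.9% | 5.2% | 81.8% | 81.8% | 84.4% |

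Type I error stays at about 5%. Against always adjusting, the conditional rule loses 0.4 to 2.6 points of power.

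**3. Bringing site into the primary analysis.** Sites of 250/200/150, OR 1.98, 6,000 replicates. The logistic model has site as a fixed effect plus two covariates at log-OR 0.3. Each cell gives simple / site-stratified allocation:

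| Control quit rates by site | Chi-square | CMH | Logistic |
|---|---|---|---|
| 10/10/10% | 80.8 / 81.2% | 80.6 / 81.2% | 81.5 / 81.6% |
| 5/10/15% | 75.7 / 76.2% | 76.5 / 76.8% | 77.2 / 77.7% |
| 5/15/30% | 83.3 / 83.9% | 86.5 / 86.0% | 87.2 / 86.6% |

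The logistic model gains between 0.4 points (81.6 − 81.2) and 3.9 points (87.2 − 83.3). Null error was 4.5–5.4% for CMH and 4.6–5.3% for the logistic model. With site and a single covariate (log-OR 0.30 or 0.45, OR 2, 5,000 trials each), the gain over chi-square was 0.3–0.6 points with equal site rates, 0.7–0.9 at 6/10/15% and 2.7–3.9 at 3/8/20%.

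**4. GEE with site as cluster, no true effect.** Simulated type I error:

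| Variance and reference | Type I error |
|---|---|
| Uncorrected sandwich, z, independence (eight scenarios, 20,000 replicates each) | 25.1–27.4% |
| Uncorrected sandwich, z, exchangeable (1,000 replicates per scenario) | 24.4–26.1% |
| Bias-reduced sandwich, z | 13–14% |
| Uncorrected sandwich, t on 2 df | 7.2–8.3% |
| Sandwich variance × 3/2, t on 2 df | 5.0–5.8% |
| Model-based standard error | 4–6% |
| CMH by site, for comparison | 4.9–5.2% |

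A rough analytic check agrees. With three similar clusters the uncorrected sandwich averages 2/3 of the true variance and carries 2 df, so the test statistic behaves like √1.5 × t on 2 df, and P(|t| > x) = 1 − x/√(2 + x²).

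- z reference: x = 1.96/√1.5 = 1.600, giving 1 − 1.600/√4.561 = 25.1%.
- t reference (critical value 4.303): x = 4.303/√1.5 = 3.513, giving 1 − 3.513/√14.34 = 7.2%.

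**The case against.** The strongest defence is that nothing here threatens the primary test, and most of it stands.

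- **The plan does not say that the primary test switches.** A reader might infer that the logistic model replaces the chi-square once imbalance is seen. The chi-square is stated unconditionally and the regression is added to it; precedence is simply missing. Nor does the trigger inflate type I error, even when the better of the two results is picked (step 2).
- **The plan does not commit to a test with 25% error.** A reader might infer this from the mention of GEE. CMH is named first in that sentence, it holds 5%, and exploratory analyses stratified by site are also planned. The GEE is something to consider as a sensitivity analysis, with no variance estimator, working correlation or reference distribution fixed. The 25% belongs to an uncorrected sandwich with a z reference.
- **The power loss is not large.** A reader might infer otherwise from a scenario with six independent predictors at log-OR 0.45 each, where power at OR 2 is 74% unadjusted, 75% with the trigger and 80% with prespecified adjustment. The documents give no support for predictors that strong, and site plus cigarettes per day would not deliver that gain. At log-OR 0.30 the same scenario gives 77%, 78% and 79%.
- **Variation between sites is assumed.** The documents give no site-specific quit rates.

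What the defence leaves untouched is the missing criterion, covariate list and precedence, and the absence of site from the primary analysis.

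**Conclusion.** The point holds in a limited form. The main cessation result, and by the same rule the quit-attempt result, is not fixed in advance: chance imbalance settles whether an adjusted odds ratio is reported and on which covariates. Site, a design feature known before the first patient, is left to an optional sensitivity analysis in which a sound method and a fragile one are offered as equals.

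The cost is mainly in interpretation. Type I error of the primary test is about 5% under every rule examined. The remedy gains about 0 to 4 points of power, and the top of that range needs quit rates that differ widely between sites. The 25% figure applies only if the three-cluster GEE is run uncorrected with a z reference. All simulated figures assume a two-sided 5% level, quit rates and covariate strengths that the documents do not state. The sentence on regression for cigarettes per day breaks off in the available text and was not used.

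**What to change.** Prespecify one primary analysis, whatever balance is observed:

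1. Fit a logistic regression of 6-month cessation on arm, site (fixed effect) and pre-randomization cigarettes per day from the PRO. Report a standardized risk difference with 95% CI: the mean predicted probability with everyone assigned to AT, minus that with everyone assigned to eTAU. If a simple test is preferred, use CMH stratified by site.
2. Apply the same analysis to 24-hour quit attempts.
3. Keep the unadjusted chi-square as a sensitivity analysis.
4. Delete the imbalance trigger and the GEE with site as cluster, and describe site as a stratum.

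The PRO value is the safer covariate because it precedes randomization. Under Questionnaire Completion, the study questionnaires may be filled in after the provider visit, by which time the intervention-arm provider may already have the medication recommendation.

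The cost is SAP wording only, since site and the PRO smoking items are already captured. The model has few terms: at 10% v 18% there would be 30 + 54 = 84 quitters for four coefficients besides the intercept. One downside is that the Informed Consent text lets a patient enrol on a PRO up to 6 months old. An older value costs some precision but not validity.

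### Cigarette reduction: baseline adjustment should be the unconditional main analysis, because the unadjusted change-score default gives up precision for no saving

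*Combined protocol and SAP*

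**What the plan says.** Aim 1 (Purpose and Background) names biochemically confirmed abstinence as the primary outcome. It also hypothesises a larger fall in the mean daily cigarette count at six months.

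For that second outcome, the Data Analysis section states that "we will look at the change in number of cigarettes smoked per day at baseline and 6-month follow-up". A two-sample t-test or a rank-sum test, whichever is judged appropriate, is used to "test for a difference in the change in cigarettes per day between the 2 groups". No rule for choosing between the two is visible. Regression comes next, as a conditional step: "If necessary, an ordinary least squares regression model with change in cigarettes per day as the outcome adjusting for baseline". The text available for this review breaks off there, so any further covariates and any definition of the trigger cannot be seen. That gap comes from how the text was extracted and is not held against the plan.

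Three other statements bear on the point:

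- Baseline cigarettes per day is already collected. Eligibility requires "Smoking 5 or more cigarettes per day for the past month", and the plan ends with "Exploratory analyses will be conducted stratified by site, cigarettes per day at enrollment, and quit goal".
- The section lists longitudinal models using every visit, but as additions to the main tests.
- Participants with no 6-month data are counted as smokers. Leaving them out is described as a sensitivity analysis.

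**The concern.** The possible change depends on where a participant starts. A 30-a-day smoker can fall by 30, while someone at the entry threshold of 5 can fall by at most 5. An unadjusted comparison of change scores treats that baseline-driven spread as noise, and a chance baseline difference between the arms shifts the estimate. Regression on baseline removes the part of this that baseline predicts, using a variable the trial already holds.

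There is also a question of what is estimated. The t-test compares means and the rank-sum test compares distributions, while Aim 1 is stated for the mean. With no visible rule for choosing the test, or for when adjustment is needed, the reported effect measure could be settled after the data are seen.

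At stake are the width of the confidence interval and the power for one Aim 1 hypothesis.

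**Working it through.** **Inputs from the documents.** Total enrolment is 600 (250 + 200 + 150), allocated 1:1, so 300 per arm. The plan gives no power, effect size, SD, correlation or alpha for this outcome, so it has no figure of its own to reproduce.

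**Assumptions.** Two-sided 5% test, 80% power as a reference point, and baseline to 6-month correlation r of 0.3 to 0.7. Results are in SD units.

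**Step 1: general result.** Let s0 and s6 be the within-arm SDs at baseline and 6 months.

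- Var(change) = s0² + s6² − 2·r·s0·s6
- Var(adjusted) = s6²·(1 − r²)
- Difference = s0² − 2·r·s0·s6 + r²·s6² = (s0 − r·s6)²

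The difference is never negative. It is zero only when r·s6/s0, the slope of follow-up on baseline, equals 1.

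**Step 2: equal SDs.** The variances are 2(1 − r)s² and (1 − r²)s², so the ratio adjusted/change is (1 + r)/2. The power column takes the difference at which the change-score t-test has 80% power with 300 per arm and computes Φ(2.80/√ratio − 1.96).

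| r | Var(change)/s² | Var(adjusted)/s² | Ratio | Adjusted n per arm matching 300 on change | Power of adjusted model |
|---|---|---|---|---|---|
| 0.3 | 1.40 | 0.91 | 0.65 | 195 | 93.5% |
| 0.5 | 1.00 | 0.75 | 0.75 | 225 | 89.9% |
| 0.7 | 0.60 | 0.51 | 0.85 | 255 | 86.0% |

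At r = 0.5 the difference detectable with 80% power is 2.80·√(2 × 1.00/300) = 0.229 SD on change, and 0.229·√0.75 = 0.198 SD with adjustment. The variance ratio does not depend on how many participants are lost.

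**Step 3: unequal SDs.** With k = s6/s0, the ratio is k²(1 − r²)/(1 + k² − 2rk).

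| k | r = 0.3 | r = 0.5 | r = 0.7 |
|---|---|---|---|
| 0.7 | 0.417 | 0.465 | 0.490 |
| 0.85 | 0.542 | 0.621 | 0.692 |
| 1.2 | 0.762 | 0.871 | 0.966 |
| 1.5 | 0.871 | 0.964 | 0.998 |

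The gain is larger if 6-month counts are less variable than baseline counts. It nearly vanishes if they are more variable and strongly correlated with baseline. At k = 1.25 and r = 0.8 it is exactly zero: 1 + 1.5625 − 2.00 = 0.5625 for change, and 1.5625 × 0.36 = 0.5625 for the adjusted model.

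**Step 4: the rank-sum branch.** No comparable inequality covers it, so it was simulated: skewed baseline counts with a minimum of 5, quitters set to zero at 6 months, 300 per arm, 2,000 trials per row. The adjusted model used ordinary model-based standard errors. All settings are assumptions.

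| Quit rate, control / intervention | Extra cut in continuing smokers, intervention | Observed r | t-test | Rank-sum | Adjusted |
|---|---|---|---|---|---|
| 8% / 15% | 8% | 0.29 | 0.65 | 0.69 | 0.87 |
| 8% / 15% | 8% | 0.45 | 0.78 | 0.81 | 0.91 |
| 8% / 15% | 8% | 0.61 | 0.90 | 0.95 | 0.96 |
| 8% / 8% | 12% | 0.48 | 0.62 | 0.73 | 0.80 |
| 8% / 18% | none | 0.44 | 0.47 | 0.44 | 0.63 |
| 10% / 10% (null) | none | 0.46 | 0.041 | 0.035 | 0.046 |

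The adjusted model had more power than rank-sum in all five alternatives, by about 2 to 19 percentage points, and held its level under the null.

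**The case against.** The strongest reply is that the plan may already contain the right estimator. If the broken-off sentence goes on to name baseline cigarettes per day, then regressing change on arm and baseline gives the same treatment estimate and standard error as regressing the 6-month count on arm and baseline. What would remain is its rank: a conditional fallback instead of the main analysis. That is correct, and it makes the fix smaller. It does not remove the point, because the conditional wording is visible. If the sentence refers only to other imbalanced variables, the gain is not assured.

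A second reply is that the longitudinal models and the stratification by enrolment smoking already use baseline information. They do, but only as additional or exploratory analyses. No unconditional baseline-adjusted 6-month contrast is visible.

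A third is that the consequence is limited. This stands. Under randomization, chance imbalance causes neither bias nor type I error inflation in a prespecified change-score test, and the abstinence analysis is unaffected.

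Two stronger readings are tempting and should be resisted:

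- **That change scores lose precision whenever the correlation is below 1.** This is true with equal SDs but not in general, as k = 1.25 with r = 0.8 shows.
- **That the outcome is silently analysed on complete cases.** Counting missing participants as smokers supplies no cigarette count. But the plan makes excluding them a sensitivity analysis, which implies that the main analysis keeps them. What can be said is that no way of filling the missing count is visible.

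**Conclusion.** The point holds as a matter of precision and prespecification for an Aim 1 outcome that is not the named primary. Against the t-test on change, adjustment for baseline asymptotically cannot lose and usually gains. With equal SDs the variance falls by 35%, 25% or 15% at r = 0.3, 0.5 or 0.7. Put the other way, change scores need about 54%, 33% or 18% more participants for the same precision (1/0.65, 1/0.75, 1/0.85).

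These figures rest on assumed correlations and on equal SDs, neither of which the documents give. With unequal SDs the gain runs from larger than this to almost nil. Against rank-sum, a gain is likely on the simulated evidence but is not guaranteed for every distribution. A reader might infer that the planned test is biased or that the trial's primary conclusion is at risk; the documents support neither.

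**What to change.** In the Data Analysis section:

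1. Make the baseline-adjusted linear model the main analysis of cigarette reduction, without condition: 6-month cigarettes per day (or, equivalently, change) on arm and baseline cigarettes per day, with robust standard errors.
2. State that baseline is the pre-randomization value and name its source. This matters because the enrolment questionnaires may be completed after the provider visit (Questionnaire Completion), whereas the screening record precedes consent and randomization.
3. Report the adjusted mean difference with its 95% CI, which matches the mean named in Aim 1.
4. Keep the rank-sum test on change as a sensitivity analysis, and drop the data-dependent choice of test.
5. For missing 6-month counts, name the longitudinal model already listed, with baseline adjustment, as the supporting analysis.

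The cost is wording only. The variables are already collected, and no extra participants or visits are needed.
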